**Also reported on OSI-774 (erlotinib) trials but with the relationship to OSI-774 (erlotinib) still undetermined:**

**BLOOD AND LYMPHATIC SYSTEM DISORDERS** - Disseminated intravascular coagulation

**EYE DISORDERS** - Blurred vision; Eye disorders - Other (orbital cellulitis); Uveitis; Watering eyes

**GASTROINTESTINAL DISORDERS** - Colitis; Constipation; Duodenal ulcer; Dysphagia; Esophagitis; Gastric ulcer; Gastritis; Gastrointestinal disorders - Other (pneumatosis intestinalis); Pancreatitis

**GENERAL DISORDERS AND ADMINISTRATION SITE CONDITIONS** - Edema limbs

**HEPATOBIILIARY DISORDERS** - Cholecystitis

**INVESTIGATIONS** - Creatinine increased; INR increased (in patients taking Coumadin); Lymphocyte count decreased; Platelet count decreased

**METABOLISM AND NUTRITION DISORDERS** - Hyperglycemia; Hyperkalemia; Hypocalcemia; Hypokalemia; Hypomagnesemia; Hyponatremia; Hypophosphatemia

**MUSCULOSKELETAL AND CONNECTIVE TISSUE DISORDERS** - Generalized muscle weakness

**NERVOUS SYSTEM DISORDERS** - Dizziness; Ischemia cerebrovascular; Peripheral sensory neuropathy

**PSYCHIATRIC DISORDERS** - Confusion

**RENAL AND URINARY DISORDERS** - Acute kidney injury

**RESPIRATORY, THORACIC AND MEDIASTINAL DISORDERS** - Adult respiratory distress syndrome; Pharyngolaryngeal pain

**SKIN AND SUBCUTANEOUS TISSUE DISORDERS** - Urticaria

**VASCULAR DISORDERS** - Thromboembolic event

**Note:** OSI-774 (erlotinib) in combination with other agents could cause an exacerbation of any adverse event currently known to be caused by the other agent, or the combination may result in events never previously associated with either agent.

**Note:** OSI-774 (erlotinib)-induced diarrhea and/or vomiting has been associated with dehydration, hyperkalemia; hypocalcemia; hypokalemia; hypomagnesemia; hyponatremia; hypophosphatemia, increased creatinine, and renal failure.

**Note:** Cases of hepatic failure and hepatorenal syndrome (including fatalities) have been reported during use of OSI-774 (erlotinib) in patients with baseline hepatic impairment.

**Warning:** Treatment with erlotinib should be used with extra caution in patients with total bilirubin > 3 x ULN. Patients with hepatic impairment (total bilirubin > ULN or Child-Pugh A, B and C) should be closely monitored during therapy with erlotinib. Erlotinib dosing should be interrupted or discontinued if changes in liver function are severe such as doubling of total bilirubin and/or tripling of transaminases in the setting of pretreatment values outside normal range.

**Warning:** Cases of hepatic failure and hepatorenal syndrome (including fatalities) have been reported during use of erlotinib, particularly in patients with baseline hepatic impairment. Therefore, periodic liver function testing (transaminases, bilirubin, and alkaline phosphatase) is recommended. In the setting of worsening liver function tests, dose interruption and/or dose

reduction with frequent liver function test monitoring should be considered. Erlotinib dosing should be interrupted or discontinued if total bilirubin is  $> 3 \times \text{ULN}$  and/or transaminases are  $> 5 \times \text{ULN}$  in the setting of normal pretreatment values.

**Warning:** Cases of hepatorenal syndrome, acute renal failure (including fatalities), and renal insufficiency have been reported. Some were secondary to baseline hepatic impairment while others were associated with severe dehydration due to diarrhea, vomiting, and/or anorexia or concurrent chemotherapy use. In the event of dehydration, particularly in patients with contributing risk factors for renal failure (e.g., pre-existing renal disease, medical conditions or medications that may lead to renal disease, or other predisposing conditions including advanced age), erlotinib therapy should be interrupted and appropriate measures should be taken to intensively rehydrate the patient. Periodic monitoring of renal function and serum electrolytes is recommended in patients at risk of dehydration.

**Gastrointestinal Perforation:** Patients receiving erlotinib are at increased risk of developing gastrointestinal perforation, which was observed uncommonly. Some cases had a fatal outcome. Patients receiving concomitant anti-angiogenic agents, corticosteroids, NSAIDs, and/or taxane based chemotherapy, or who have prior history of peptic ulceration or diverticular disease, are at increased risk. Erlotinib should be permanently discontinued in patients who develop gastrointestinal perforation.

**Bullous and Exfoliative Skin Disorders:** Bullous, blistering and exfoliative skin conditions have been reported, including very rare cases suggestive of Stevens-Johnson syndrome/Toxic epidermal necrolysis, which in some cases were fatal. Erlotinib treatment should be interrupted or discontinued if the patient develops severe bullous, blistering, or exfoliating conditions.

**Ocular Disorders:** Very rare cases of corneal perforation or ulceration have been reported during use of erlotinib. Other ocular disorders including abnormal eyelash growth, keratoconjunctivitis sicca or keratitis have been observed with erlotinib treatment and are known risk factors for corneal perforation/ulceration. Erlotinib therapy should be interrupted or discontinued if patients present with acute/worsening ocular disorders such as eye pain.

Potential Drug Interactions: Erlotinib is both protein bound (92% to 95%) and metabolized by CYP3A4. Therefore, a potential for drug-drug interactions exists when erlotinib is co-administered with drugs that are highly protein-bound or CYP3A4 inhibitors or inducers.

There is a potential interaction between erlotinib and warfarin. Patients have experienced elevated INRs and bleeding with this combination of drugs. Patients on warfarin and erlotinib should have more frequent INR/PT determinations (e.g., weekly for the first month and weekly for a minimum of 2 weeks following discontinuation erlotinib).

**Proton Pump Inhibitor:** Erlotinib's solubility decreases as the pH increases. Co-administration of omeprazole with erlotinib will decrease the AUC and  $C_{\max}$  by 46% and 61%, respectively.

H2-antagonist: Avoid concomitant use of erlotinib with gastric acid reducing agents if possible. When ranitidine 300 mg is given with erlotinib, erlotinib AUC and Cmax decrease by 33% and 54%, respectively. Increasing the dose of erlotinib will not compensate the loss of exposure. However, if an H2-antagonist receptor is needed, take erlotinib at least 2 hours before or 10 hours following the H2-antagonist administration. Dosing such, erlotinib loss of exposure is minimized to AUC of 15% and Cmax of 17%.

Patient Care Implications: If the patient vomits after taking the tablets, the dose is replaced only if the tablets can actually be seen and counted.

Patients should wear sun screen protection, hat, and long sleeves to avoid sun as it can exacerbate skin rash.

Patients should be advised to stop smoking while taking erlotinib. Smoking induces CYP1A2 enzymes and alters erlotinib exposure by 64%

Pregnancy and Lactation: No information on pregnancy and lactation in humans is available yet.

c. PHARMACOLOGY

Total clearance of erlotinib is similar to hepatic blood flow in dogs and rats. At intravenous doses > 1 mg/kg the clearance decreases and the plasma drug exposure increases supra-proportionately in rats and dogs. In vitro, the agent is slowly oxidized by liver microsomes. Erlotinib is extensively metabolized in rats and dogs with only a small amount excreted unchanged in urine, bile and feces. In a rat model designed to study pulmonary first pass extraction, erlotinib had a pulmonary extraction of approximately 48%. In vitro studies have shown that the agent is metabolized by CYP1A1, which is expressed in lung tissue. Several circulating metabolites have been identified in mouse, rat and dog and subsequently synthesized and demonstrated to be potent as EGFR inhibitors. Only one, OSI-420, a hydroxylated metabolite, was a major metabolite in systemic circulation with a metabolite: parent ratio of 1:4 in plasma from rats or dogs given oral doses. This compound is as potent as erlotinib in the in vivo tumor xenograft model.

The enzymes responsible for formation of the major metabolite in humans were identified as cytochromes P450 3A4 and 3A5 (expressed in liver) and 1A1 (expressed in lung). Studies on the inhibition potential of erlotinib and its major metabolite, OSI-420, on the main human cytochrome P450 isoenzymes revealed a relatively strong inhibition of CYP 3A4 by erlotinib (Ki 8 μM) and a weak inhibition of CYPs 1A2 and 3A4 by OSI-420 (Ki 20 μM). Further studies to evaluate the mechanism of inhibition are ongoing.

Oral bio-availability was found to be 77% in rats and 88% in dogs. Plasma protein binding is 92 - 95% in humans, rats, monkeys and mice, and was 85% in dogs.

How Supplied: Erlotinib is supplied as 25 mg, 100 mg, and 150 mg white film-coated tablets. In addition to the active ingredient, erlotinib, the tablets contain lactose, microcrystalline cellulose, sodium starch glycolate, sodium lauryl sulfate, and magnesium stearate. Tablets are unmarked and unscored. The 25 mg tablets [1/4 inch diameter, 3 mm deep (formerly non-film coated)], 100 mg tablets (11/32 inch diameter, 5 mm deep), and 150 mg tablets (13/32 inch diameter, 5.1 mm deep) are supplied 30 tablets/bottle.

Storage and Stability: Store in accordance with the package labeling. Shelf life surveillance studies of the intact bottle are on-going. Current data indicates erlotinib is stable for at least 3 years at room temperature.

Administration: Erlotinib is administered orally. Tablets should be taken once daily preferably in the morning with up to 200 mL of water one hour before or two hours after food.

d. SUPPLIER

Erlotinib is an investigational agent supplied to investigators by the Division of Cancer Treatment and Diagnosis (DCTD), NCI. Erlotinib is provided to the NCI under a Clinical Trials Agreement between OSI Pharmaceuticals and the NCI Division of Cancer Treatment and Diagnosis (DCTD).

Drug Ordering: NCI supplied agents may be requested by the Principal Investigator (or their authorized designee) at each participating institution. Pharmaceutical Management Branch (PMB) policy requires that agent be shipped directly to the institution where the patient is to be treated. PMB does not permit the transfer of agents between institutions (unless prior approval from PMB is obtained). The CTEP assigned protocol number must be used for ordering all CTEP supplied investigational agents. The responsible investigator at each participating institution must be registered with CTEP, DCTD through an annual submission of FDA form 1572 (Statement of Investigator), Curriculum Vitae, Supplemental Investigator Data Form (IDF), and Financial Disclosure Form (FDF). If there are several participating investigators at one institution, CTEP supplied investigational agents for the study should be ordered under the name of one lead investigator at that institution.

Drug may be requested by submitting agent requests through the PMB Online Agent Ordering Processing (OAOP) application (<https://eapps-ctep.nci.nih.gov/OAOP/pages/login.jsp>). Access to OAOP requires the establishment of a CTEP Identity and Access Management (IAM) account (<https://eapps-ctep.nci.nih.gov/iam/>) and the maintenance of an "active" account status and a "current" password.

Drug Returns: All unused drug supplies should be returned to the PMB. When it is necessary to return study drug (e.g. sealed vials remaining when expired vials are recalled by the PMB), investigators should return the study drug to the PMB using the NCI Return Agent Form available on the NCI home page (<http://ctep.cancer.gov>).

Drug Accountability: The investigator, or a responsible party designated by the investigator, must maintain a careful record of the receipt, disposition and return of all drugs received from the PMB using the Drug Accountability Record Form available on the NCI home page (<http://ctep.cancer.gov>).

Questions about drug orders, transfers, returns or accountability should be addressed to the PMB by calling [name] Monday through Friday between 8:30 a.m. and 4:30 p.m. Eastern time by emailing [[contact]](mailto:[contact]) anytime.

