### 8.3 Patient Evaluations

Patients will be evaluated every two weeks for the first eight weeks and then once every four weeks to determine toxicities and the appropriate dose modification (decrease, hold, or discontinue). If all protocol treatment is delayed more than three weeks, patients will be removed from protocol treatment.

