### 8.5 ARQ 197 Dose Modification

If ARQ 197 is held, erlotinib will also be held for patients on Arm 2 and resumed at the same time treatment with ARQ 197 is resumed. There will be no dose reduction of erlotinib if the toxicity was thought to be related to ARQ 197.

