#### a. Hematologic toxicities:

Absolute neutrophil count (ANC) ( $\times 10^6/L$ )	Platelets ( $\times 10^6/L$ )	ARQ 197
$\geq 1,000$ and	$\geq 75,000$	100% dose
$< 1,000$ or	$< 75,000$	*Hold until ANC $\geq 1,000$ and platelets $\geq 75,000$ and reduce to the next lower dose level

\* Treatment may be held up to 21 days and can be resumed at the next lower dose level once ANC is  $\geq 1000 \times 10^6/L$  and platelet count is  $\geq 75,000 \times 10^6/L$ . Patients who cannot tolerate ARQ 197 at 120 mg BID will be removed from the protocol. No dose re-escalation is allowed.

CLOSED TO PUBLIC 05/29/2014

b. Non-hematologic toxicities:

The following modifications should be followed in the event of ARQ 197 related-non-hematologic toxicity.

Toxicity Grade(NCI CTCAE v4.0)	Percent of full dose of ARQ 197I
0-2	100%
3	Hold*
4	Hold*

\* Treatment may be held up to 21 days Any patient who experiences Grade 3 or greater non-hematologic toxicity which resolves to Grade 0 or 1 may be treated at a next lower dose level of ARQ 197 for subsequent doses. Patients who cannot tolerate ARQ 197 at 120 mg BID will be removed from the protocol. No dose re-escalation is allowed.

c. ARQ 197 Dose Level Reductions

Starting Dose	First Reduction	Second Reduction
360 mg BID	240 mg BID	120 mg BID

NOTE: Any patient who fails to tolerate treatment of 120 mg BID will be withdrawn from protocol treatment. If a treatment is delayed more than 21 days for the resolution of ARQ 197-related toxicities to Grade 0 or 1 patient will be removed from the protocol.

CLOSED EFFECTIVE 05/29/2014

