8.6 Erlotinib Dose Modificationa

Toxicity (NCI CTCAE v4.0)	Dose Modification
Diarrhea	
Grade 1	None. Initiate therapy with loperamide.(8.7a)
Grade 2	Hold erlotinib. Initiate loperamide until resolution to Grade 0-1. Resume therapy at the same dose.
Grade 3 b or 4 b	Hold erlotinib. Initiate therapy with loperamide and appropriate supportive care until resolution to Grade 0 or 1 and then restart at 1 dose level lower
Rash	
Grade 1	None
Grade 2	None. Initiate treatment (8.7b) . If rash persists and is intolerable or worsens over 10 – 14 days, then reduce by 1 dose level.
Grade 3	Reduce by 1 dose level. If rash persists or worsens over 10 – 14 days, then interrupt erlotinib until resolution to Grade 0, 1 or 2 and then restart 1 dose level lower.
Grade 4	Permanently discontinue erlotinib.
Interstitial Lung Disease	
Any Grade	If ILD is suspected, erlotinib should be interrupted immediately pending diagnostic evaluation. If ILD is diagnosed, erlotinib should be discontinued permanently and appropriate treatment instituted as necessary.
Other Toxicities Attributable to Erlotinib	
Grade 1 or 2	None
Grade 3 or 4 b, c	Interrupt erlotinib until resolution to Grade 0 or 1 and then restart 1 dose level lower.
Other Toxicities (hematologic and non-hematologic) attributable to ARQ 197	
Grade 1 or 2	None
Grade 3 or 4	Hold erlotinib until ARQ 197 is resumed. If toxicity was deemed related to ARQ 197 no dose reduction of erlotinib is indicated

- (a) Doses that have been reduced should not be re-escalated. Any patient who fails to tolerate treatment at 50 mg/day will discontinue erlotinib and continue on single agent ARQ 197.
- (b) If the event does not resolve to Grade 0 or 1 within 21 days, erlotinib will be discontinued and patient will continue on a single agent ARQ 197
- (c) Only if  $\geq 2$  Grade level change from baseline

Erlotinib Dose Level Reductions

Starting Dose	First Reduction	Second Reduction
150 mg/day	100 mg/day	50 mg/day

NOTE: Any patient who fails to tolerate erlotinib at 50 mg/day will continue on single agent ARQ 197. If a treatment is delayed more than 21 days for the resolution of erlotinib-related toxicities to Grade 0 or 1, discontinue erlotinib and continue ARQ 197 alone.

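### In Arm 2, transaminases that triple from a Grade 2 baseline but stay at Grade 3 meet the Section 3.2b liver warning, yet the Section 8.6 dose table prompts no erlotinib hold

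*Combined protocol and SAP*

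**What the plan says.** **Section 3.2b (erlotinib toxicology, liver warnings).** Where pretreatment values are outside the normal range: "Erlotinib dosing should be interrupted or discontinued if changes in liver function are severe such as doubling of total bilirubin and/or tripling of transaminases". Where they were normal, the limits are absolute: bilirubin above 3 x ULN and/or transaminases above 5 x ULN. For worsening liver tests in general the text is softer: interruption and/or dose "reduction with frequent liver function test monitoring should be considered".

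**Section 8.6 (erlotinib dose modification).** The named rows are diarrhea, rash and interstitial lung disease; none is hepatic. Liver tests attributed to erlotinib therefore fall under other toxicities attributable to erlotinib. Grade 1 or 2 needs no action. At Grade 3 or 4 the instruction is "Interrupt erlotinib until resolution to Grade 0 or 1 and then restart 1 dose level lower". Footnote (c) restricts this to at least a 2 "Grade level change from baseline". Footnote (b) adds: "If the event does not resolve to Grade 0 or 1 within 21 days, erlotinib will be discontinued", with ARQ 197 continuing alone.

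**Section 8.5 (ARQ 197 dose modification).** Section 8.5b holds ARQ 197 at Grade 3 with no condition on change from baseline; "Any patient who experiences Grade 3 or greater non-hematologic toxicity which resolves to Grade 0 or 1" may resume one dose level lower. The opening of 8.5 adds: "If ARQ 197 is held, erlotinib will also be held for patients on Arm 2".

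**Section 5.3d (eligibility).** AST and ALT may be up to 1.5 x ULN, or up to 5 x ULN if the tumor involves the liver. Bilirubin may be up to 1.5 x ULN.

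**The concern.** The 3.2b warning is relative to the patient's own baseline and carries no grade condition. The 8.6 row works by grade and by number of grades moved. When the baseline is already Grade 2, reaching Grade 3 is a one-grade move. If that move is also a tripling, 3.2b says to interrupt or discontinue, while 8.6 prompts nothing.

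Section 3.2b reports hepatic failure, including deaths, particularly with baseline hepatic impairment. A site that doses from 8.6 alone could therefore continue full-dose erlotinib in the group that the protocol itself marks as higher risk. Section 8.7 repeats the 3.2b cautions on dehydration, skin and eyes beside the dose table but omits the liver warning, and 8.6 does not refer back to 3.2b.

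The outcome also depends on attribution. The same Grade 2 to Grade 3 rise blamed on ARQ 197 holds both drugs under 8.5. Blamed on erlotinib, the tables hold neither.

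**Working it through.** The plan prints no figure on this point, so the check compares two rules over the baselines that eligibility allows.

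**Inputs**
- 3.2b trigger, abnormal baseline b (in x ULN): transaminases at 3b, bilirubin at 2b.
- 8.6 residual row with footnote (c): hold only if grade is at least 3 and (grade minus baseline grade) is at least 2.
- 5.3d: AST/ALT b up to 5 with liver involvement, otherwise up to 1.5; bilirubin b up to 1.5.
- Grade limits: Section 8.1 names CTCAE v4.0 but prints no limits. **Assumed:** AST/ALT Grade 1 >1, Grade 2 >3, Grade 3 >5, Grade 4 >20 x ULN; bilirubin >1, >1.5, >3, >10 x ULN.

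**Step 1, from the protocol text.** Grade 2 to Grade 3: 3 - 2 = 1, below 2, so 8.6 prompts no hold. Grade 2 to Grade 4: 4 - 2 = 2, so it does.

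**Step 2, tripled AST/ALT under the assumed limits.** The first band ends where 3b = 5, at b = 5/3 = 1.67.

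| Baseline (x ULN) | Grade | Tripled value | Grade | 3.2b | 8.6 |
|---|---|---|---|---|---|
| >1 to 1.67 | 1 | >3 to 5 | 2 | met if judged severe | no action |
| >1.67 to 3 | 1 | >5 to 9 | 3 | interrupt or discontinue | hold |
| >3 to 5 | 2 | >9 to 15 | 3 | interrupt or discontinue | no hold |

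The third row is the conflict.

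**Step 3, its width.** With a Grade 4 limit L, width = max(0, L - 3b). At L = 20:
- b just above 3: 20 - 9 = 11
- b = 4: 20 - 12 = 8
- b = 5: 20 - 15 = 5

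So 8.6 acts only at about 20/3 = 6.7, 20/4 = 5 and 20/5 = 4 times baseline, against 3 times in 3.2b.

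**Step 4, sensitivity to the assumed limits.**

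| L (x ULN) | b just above 3 | b = 4 | b = 5 |
|---|---|---|---|
| 20 | 11 | 8 | 5 |
| 15 | 6 | 3 | 0 |
| 12 | 3 | 0 | 0 |
| 10 | 1 | 0 | 0 |
| 9 or below | 0 | 0 | 0 |

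The conflict also vanishes if Grade 2 began at 5 x ULN or higher, since no eligible baseline would then be Grade 2. If Grade 2 began at 2.5, the width would reach 20 - 7.5 = 12.5.

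**Step 5, rises that are not a tripling.** From 4 to 6 x ULN is Grade 2 to Grade 3, but 6/4 = 1.5. Section 3.2b then only asks that interruption or reduction be considered, so there is no direct conflict.

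**Step 6, near-normal baselines.** AST/ALT of 1.1 tripled is 3.3, below the limit of 5 that 3.2b sets for normal baselines. Bilirubin of 1.1 doubled is 2.2, below 3. Whether such changes are severe is a clinical judgment, and I do not count them as conflict.

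**Step 7, how many patients.** The share of Arm 2 with baseline AST/ALT above 3 x ULN is not given. Assumed shares of 1%, 5% and 10% of the 35 eligible patients give 0.35, 1.75 and 3.5. Only those whose values then triple, stay at Grade 3 and are attributed to erlotinib would meet the conflict.

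**The case against.** The strongest reply is that both instructions can be followed. Section 3.2b is current protocol text, and nothing in 8.6 forbids a hold. Other erlotinib triggers also sit outside the 8.6 table: dehydration, skin and eye events in 8.7, and gastrointestinal perforation in 3.2b. Requiring a change from baseline is a reasonable way to handle patients whose liver tests are raised by tumor, and separate rules by attributed drug are a legitimate design choice. Monitoring is frequent: "Patients will be evaluated every two weeks for the first eight weeks and then once every four weeks to determine toxicities". Attribution to ARQ 197, alone or jointly, removes the conflict, and Section 2.0 reports Grade 3 or greater ALT and AST elevations (3% each) possibly or probably related to that drug.

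Most of this stands, and it limits the point. A reader might infer that 8.6 bars a hold; it does not. A reader might also infer that every Grade 2 to Grade 3 rise is a conflict; Step 5 shows that only rises of at least three times baseline are.

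What remains is that permission differs from a prompt. The frequent visits exist to apply the dose rules, and for these patients the rule in the table gives a different answer from the warning. Nor is attribution to ARQ 197 assured: Section 3.1b lists AST and ALT increases for ARQ 197 as having insufficient evidence, while 3.2b lists them as possibly related to erlotinib.

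**Conclusion.** The inconsistency is real but narrow. It concerns Arm 2 patients with a Grade 2 transaminase baseline whose values at least triple, stay at Grade 3, and are attributed to erlotinib. Under the assumed limits these are baselines of >3-5 x ULN, reaching >9-15 x ULN when tripled, with no prompt from 8.6 until above 20 x ULN.

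The one-grade logic comes from the protocol alone. A reader might infer that the documents also prove an eligible patient can be affected. They do not: that step needs the CTCAE limits, which are assumed here, and Step 4 shows where the conflict shrinks or disappears.

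Few patients are likely to be affected, and the number cannot be derived from the documents. Alpha, power and sample size are untouched. I rate this a minor safety consistency fix.

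**What to change.** Add a liver row to 8.6 for tests attributed to erlotinib when the baseline is abnormal:
- Interrupt or discontinue for severe changes such as bilirubin at 2 x baseline and/or transaminases at 3 x baseline. Keep the illustrative wording of 3.2b, and leave the choice between interrupting and discontinuing to the clinician.
- State that footnote (c) does not block this row, and that the existing Grade 3-4 trigger still applies where it acts earlier.
- Leave near-normal baselines (AST/ALT about 1 to 1.67 x ULN, bilirubin 1 to 1.5 x ULN) to clinical judgment of severity, so that they are not held more strictly than normal baselines. Because 5.3d caps bilirubin at 1.5 x ULN, this covers every eligible abnormal bilirubin baseline.
- Define recovery for this row, including the 21-day rule in footnote (b), as Grade 0-1 or baseline. Otherwise a Grade 2 patient who has fully returned to baseline would still lose erlotinib. This is a secondary matter, needed to make the row workable.

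Deleting footnote (c) for liver tests would be a different rule: a baseline of 4 x ULN would be held above 5 (5/4 = 1.25, a 25% rise) and not at 12. A bare cross-reference to 3.2b would help but would leave footnote (c) pointing the other way.

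The cost is one table row and footnote edits in one amendment. No new tests are needed, since bilirubin, SGOT and SGPT are on the Section 9.0 calendar from Week 3. The downside is a few more erlotinib holds in Arm 2, a number that the documents do not allow one to estimate. Pages are marked closed effective 05/29/2014, so only patients still on erlotinib would benefit; Revision 4 shows that drug-risk text was still being amended in 2016.
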